Based on information from similar products, the potential dose-limiting toxicity of molgramostim would be based on pulmonary effects, such as bronchoconstriction, dyspnoea, cough or decreased pulmonary function. Pulmonary function and respiratory symptoms will be monitored during the trial and double-blind trial treatment should be discontinued if significant worsening occurs. If there is significant systemic exposure, haematologic findings such as leucocytosis and neutrophilia may occur. Therefore, laboratory safety monitoring will be conducted during the Double-blind treatment period. As non-clinical data on similar products indicate that systemic exposure to rhGM-CSF may be associated with increased pre- and post-implantation losses, pregnancy testing will be performed in women of childbearing potential prior to dosing, at monthly intervals during the Double-blind treatment period and the open-label treatment Follow-up period.

Treatment with molgramostim nebuliser solution is expected to be more effective, less invasive, and more convenient, than the currently available symptomatic treatment, WLL, for patients with aPAP. In the current trial two thirds of the subjects will receive active drug and one third will receive placebo. Rescue treatment with WLL will be available for all subjects who experience any unacceptable lack of response or disease progression during the trial. Subjects requiring WLL during the Double-blind treatment period will continue trial treatment.

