10.4 Safety Assessments

10.4.1 Safety Variables

The following safety variables will be assessed:

- AEs
- Physical examination
- Vital signs
- Laboratory safety assessments
- HR-CT

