2.3 Additional Safety Endpoints

The following safety variables will be assessed:

- Physical examination during 24-weeks of treatment and 48-weeks follow-up
- Electrocardiogram during 24-weeks of treatment and 48-weeks follow-up
- Vital signs during 24-weeks of treatment and 48-weeks follow-up
- Laboratory safety assessments during 24-weeks of treatment and 48-weeks follow-up

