CT scans will be centrally evaluated by two independent and blinded assessors at the 24 weeks treatment visit where change in relation to the baseline assessment will be graded as: *Improved, Worsened, No change, Data missing or Impossible to evaluate*. This evaluation, as well as the Ground-Glass Opacification (GGO) score for each anatomical area (upper, middle and lower), (graded as: *no GGO, less than 5%, 5-24%, 25-49%, 50-74%, 75% or more GGO*) will be summarized in frequency tables by treatment group including proportion

of subjects reaching each grade. The number of subjects with, and without, improvements will be analyzed (see, below).

Continuous endpoints

The following continuous endpoints will be analysed using the same main model (ANCOVA) as applied for primary endpoint, including all collected data irrespective of adherence to treatment regimens.

- Absolute change in VC (% predicted), haemoglobin corrected DLCO (% predicted), FEV₁ (% predicted), and FVC (% predicted), and relative change in PaO₂ from baseline after 24 weeks of treatment.
- Change from baseline in pre and post-exercise dyspnoea scores and cough scores (severity and frequency VAS scores) after 24-weeks treatment.

Categorical Endpoints

Number of subjects classified as having improvements in parameters, as defined below, will be summarised by visit in frequency tables, including cumulative counts. Logistic regression models will be applied to statistically analyse if proportion of subjects having improvements differ between treatment groups according to the same groups as applied for analyses of primary and key secondary endpoints. The logistic regressions will include the same covariates as for main analysis of primary endpoint, although with the baseline covariates corresponding to each respective endpoint. The complement in these analyses, subjects not reaching improvements according to the categorisations, will be based on the total number of subjects applicable to the FAS population.

- Number of subjects with >5 mmHg/>0.67 kPa and number of subjects with >10 mmHg/>1.33 kPa improvement in (A-a)DO₂ after 24-weeks treatment
- Number of subjects with >5 percentage points and number of subjects with >10 percentage points improvement in VC (% predicted) after 24-weeks treatment
- Number of subjects with >10 percentage points improvement in DLCO (% predicted) after 24-weeks treatment

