Table	14.2.3.20	Analysis of number of subjects with >5 percentage points improvement in VC (% predicted) compared to baseline after 24 weeks treatment (Logistic regression)		X					
Table	14.2.3.21	Number and % of subjects with >10 percentage points improvement in VC (% predicted) compared to baseline by visit during 24 weeks treatment		X					
Table	14.2.3.22	Analysis of number of subjects with >10 percentage points improvement in VC (% predicted) compared to baseline after 24 weeks treatment (Logistic regression)		X					
Table	14.2.3.23	Number and % of subjects with >10 percentage points improvement in DLCO (% predicted) compared to baseline by visit during 24 weeks treatment		X					
Table	14.2.3.24	Analysis of number of subjects with >10 percentage points improvement in DLCO (% predicted) compared to baseline after 24 weeks treatment (Logistic regression)		X					
Table	14.2.3.25	Number and % of subjects with >10 percentage points improvement in FEV1(% predicted) compared to baseline by visit during 24 weeks treatment		X					
Table	14.2.3.26	Analysis of number of subjects with >10 percentage points improvement in FEV1(% predicted) compared to baseline after 24 weeks treatment (Logistic regression)		X					
Table	14.2.3.27	Number and % of subjects with >10 percentage points improvement in FVC (% predicted) compared to baseline by visit during 24 weeks treatment		X					
Table	14.2.3.28	Analysis of number of subjects with >10 percentage points improvement in FVC (% predicted) compared to baseline after 24 weeks treatment (Logistic regression)		X					
Table	14.2.3.29	Number and % of subjects with >10% relative improvement in PaO2 compared to baseline by visit during 24 weeks treatment		X					
Table	14.2.3.30	Analysis of number of subjects with >10% relative improvement in PaO2 compared to baseline after 24 weeks treatment (Logistic regression)		X					
Table	14.2.3.31	Summary of change from baseline in SpO2 at start and the worst SpO2 oxygen desaturation and distance of walk during 6 minutes walk test (6MWT) by visit during 24 weeks treatment		X					

			SCR	DB-FAS	DB-PPS	DB-SAF	FU-FAS	FU-MOL INT	FU-SAF
Table	14.2.3.32	Number of subjects with improved tolerance to exercise (increase from baseline in distance walked ≥ 50 m) by visit during 24 weeks treatment		X					
Table	14.2.3.33	Analysis of number of subjects with improved tolerance to exercise (increase from baseline in distance walked ≥ 50 m) after 24 weeks treatment (Logistic regression)		X					

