Table	14.3.5.4	Shift tables for biochemistry laboratory measurements from baseline by visit during 24 weeks of treatment				X			
Table	14.2.5.5	Summary of urinalysis laboratory measurements (France only) by visit during 24 weeks of treatment				X			
Table	14.3.5.6	Summary of haematology laboratory measurements and corresponding changes from baseline by visit during 48 weeks of follow-up							X
Table	14.3.5.7	Shift tables for haematology laboratory measurements from baseline by visit during 48 weeks of follow-up							X
Table	14.3.5.8	Summary of biochemistry laboratory measurements and corresponding changes from baseline by visit during 48 weeks of follow-up							X
Table	14.3.5.9	Shift tables for biochemistry laboratory measurements from baseline by visit during 48 weeks of follow-up							X
Table	14.3.5.10	Summary of urinalysis laboratory measurements (France only) by visit during 48 weeks of treatment							X

			SCR	DB-FAS	DB-PPS	DB-SAF	FU-FAS	FU-MOL INT	FU-SAF
Other Safety Data									
Table	14.3.6.1	Summary of vital signs and change from baseline in vital signs by visit during 24 weeks of treatment				X			
Table	14.3.6.2	Shift tables for changes in vital signs from baseline by visit during 24 weeks of treatment				X			
Table	14.3.6.3	Shift tables for changes in Physical examination from baseline by visit during 24 weeks of treatment				X			
Table	14.3.6.4	Summary of ECG and change from baseline in ECG by visit during 24 weeks of treatment full analysis set				X			
Table	14.3.6.5	Shift tables for changes in ECG from baseline by visit during 24 weeks of treatment				X			
Table	14.3.6.6	Summary of adverse findings in CT at week 24 compared to baseline				X			
Table	14.3.6.7	Summary of vital signs and change from baseline in vital signs by visit during 48 weeks of follow-up							X
Table	14.3.6.8	Shift tables for changes in vital signs from baseline by visit during 48 weeks of follow-up							X
Table	14.3.6.9	Shift tables for changes in Physical examination from baseline by visit during 48 weeks of follow-up							X
Table	14.3.6.10	Summary of ECG and change from baseline in ECG by visit during 48 weeks of follow-up							X
Table	14.3.6.11	Shift tables for changes in ECG from baseline by visit during 48 weeks of follow-up							X
Listing	16.1.7	Randomization Scheme		X					

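### No planned output counts subjects whose FEV1, FVC, VC or DLCO fell, although Protocol 5.3 names decreased pulmonary function as a potential dose-limiting toxicity

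*SAP*

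**What the plan says.** Protocol 5.3, drawing on similar products, states that "the potential dose-limiting toxicity of molgramostim would be based on pulmonary effects, such as bronchoconstriction, dyspnoea, cough or decreased pulmonary function". It continues: "Pulmonary function and respiratory symptoms will be monitored during the trial and double-blind trial treatment should be discontinued if significant worsening occurs". No numerical meaning is attached to significant worsening.

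The visit schedule (Protocol 7.2.2, Table 1) has lung function tests at Screening, Baseline and Weeks 4, 8, 12, 16, 20 and 24. At Weeks 8, 16 and 20 they are done without blood gases or the walk test.

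Lung function appears in none of the safety lists:

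- Protocol 10.4.1, under "The following safety variables will be assessed", gives adverse events, physical examination, vital signs, laboratory tests and HR-CT.
- SAP 2.3 gives physical examination, ECG, vital signs and "Laboratory safety assessments during 24-weeks of treatment and 48-weeks follow-up".
- SAP 5.3.12 and the 14.3 outputs in SAP Appendix 1 add ECG and CT items, the last being "Summary of adverse findings in CT at week 24 compared to baseline".

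VC, DLCO, FEV1 and FVC appear in the 14.2 efficacy outputs on DB-FAS: by-visit summaries, a Week 24 ANCOVA, and responder counts and logistic regressions. For the responder counts, SAP 5.3.7 says "Number of subjects classified as having improvements in parameters, as defined below, will be summarised by visit in frequency tables, including cumulative counts". A typical output title is "Number and % of subjects with >10 percentage points improvement in FEV1(% predicted) compared to baseline by visit during 24 weeks treatment". Everyone else in the FAS forms the complement.

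**The concern.** A measurement close to a toxicity the protocol itself names, taken at every double-blind visit, is reported only as possible benefit. Vital signs, laboratory values, ECG and physical examination each get a shift table on the safety set; lung function gets none, and it is never tabulated by actual treatment on DB-SAF.

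Mean change can hide a harmful response in a minority if the majority improve. A subject who loses more than 10 percentage points falls in the same category as one who did not change. The trial could then report a gain in lung function without saying how many subjects in each arm lost it. If the question came up after unblinding, any threshold would be chosen with the results in view.

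**Working it through.** The plan states no figure on this point, so there is none to reproduce. The check has two parts.

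**1. Which outputs would show a fall in spirometry or DLCO?**

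| Output | What it gives | Number of subjects with a fall? |
|---|---|---|
| By-visit summaries (SAP 5.3.3; 14.2.3) | Minimum, quartiles, mean of change, DB-FAS | No |
| Responder tables (SAP 5.3.7) | Subjects improved against all others | No |
| Listing 16.2.6.1 | Individual values | Only if counted by hand |
| CT worsened; CT adverse findings | Imaging at Week 24 | Different measure |
| DSS shift tables | Symptoms and PaO2, Screening and Week 24 | Different measure |
| Time to WLL | Investigator-judged worsening; spirometry is not a listed criterion (Protocol 10.3.3.1) | Different measure |
| Adverse events | Falls that the investigator records as an event | Only those recorded |
| Discontinuations | Subjects who stop, with reason | Only those who stop |

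On the adverse-event route, Protocol 10.4.5 and 10.1.6 require clinically significant ECG abnormalities and detrimental CT effects to be recorded as adverse events. Protocol 10.1.2 has no such rule for lung function, and Protocol 11.6 defines no events of special interest.

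**2. How much could the planned summaries leave uncounted?**

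Input: 135 subjects randomised 1:1:1 (SAP 3.1), so 135 / 3 = 45 per arm.

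*First quartile.* It is the ordered value at position ceil(0.25 × 45) = ceil(11.25) = 12. Up to 11 subjects (11/45 = 24%) can lie below any chosen decline before the quartile does; the 12th (12/45 = 27%) moves it. The minimum shows only that at least one subject fell. By-visit tables also cannot be combined into a count of subjects who fell at any visit.

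*Effect on the mean.* Assume each decliner loses 15 points (assumed, not in the documents). The shift in the arm mean is −15 × k/45:

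- k = 2: −0.67
- k = 5: −1.67
- k = 11: −3.67

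*Illustration (all rates and sizes assumed).* A proportion p of active subjects lose 15 points and the rest gain 4. On placebo 2% lose 15 and the rest do not change.

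- Active mean = −15p + 4(1 − p) = 4 − 19p. At p = 0.12 this is +1.72.
- Placebo mean = 0.02 × (−15) = −0.30.
- Difference = 1.72 + 0.30 = 2.02 points in favour of active.
- Expected decliners: 0.12 × 45 = 5.4 against 0.02 × 45 = 0.9, about 5 against 1.
- Range: the active mean stays above placebo while 4 − 19p > −0.30, that is p < 4.30/19 = 0.226, or about 10 of 45 subjects.

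*What the missing count could show.* For 5/45 against 1/45 the difference is 11.1% − 2.2% = 8.9 points. The simple standard error is √(0.111 × 0.889/45 + 0.022 × 0.978/45) = 0.052, so the 95% interval is about −1 to 19 points. Such a table would describe the harm side; it would not prove it.

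**The case against.** **Deterioration is counted in several places.** CT worsening, CT adverse findings on the safety set, DSS shifts in both directions, clinical worsening that meets the lavage criterion, adverse events and discontinuations are all tabulated by arm. A reader might infer that subjects who deteriorate on drug are never counted, or that the SAP counts only improvements. Neither is supported. The one-directional counting applies to the responder endpoints, and the very table quoted from 14.3 counts adverse findings. What stands is narrower: none of these counts a fall in spirometry or DLCO.

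**The toxicity is potential, not expected.** Protocol 5.3 says potential and gives decreased pulmonary function as one of four examples. The phase 1 study reported no dose-limiting toxicity (Protocol 5.1). This is correct and limits how strongly the point can be put.

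**The protocol promises monitoring, not a table.** Testing at every visit, diary-card questions on lung toxicity that the investigator reviews, and DSMB review of unblinded safety data can meet that promise. A reader might infer that the SAP contradicts the protocol. It does not: the protocol's own list of safety variables omits lung function and the SAP follows it. This is a reporting gap.

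**The extra table is an imperfect detector.** Spirometry is not timed to dosing, so acute bronchoconstriction may be missed. An any-visit count takes the worst of six visits for each of four variables, so noise alone creates some decliners, and DLCO uses local equipment. Disease progression also produces falls. These limits stand. The concurrent placebo arm, measured on the same schedule, largely handles noise and progression in the comparison; it does not help with dose timing.

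**Conclusion.** The point holds as a reporting gap. No planned output states how many subjects per arm had a fall in FEV1, FVC, VC or DLCO, and lung function is not tabulated on the safety set by actual treatment. Falls are visible in the minimum, the first quartile and Listing 16.2.6.1, and some will surface as adverse events, but they are not counted.

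The size of any masked harm cannot be known from the documents. The 24% bound on the first quartile follows from 45 per arm with complete data at a visit. The example of 12% against 2%, with −15 and +4 points, is purely an assumed illustration.

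The primary analysis, the sample size and the type I error control are untouched. The change should be made before unblinding, because a threshold set afterwards would carry less weight.

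**What to change.** Add to SAP Appendix 1, 14.3 'Other Safety Data', a descriptive table on DB-SAF by actual treatment, with matching text in SAP 5.3.12:

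- number and percentage of subjects with a fall of more than 10 percentage points from Baseline in each of FEV1, FVC, VC and DLCO (% predicted);
- at each double-blind visit, and at any post-baseline double-blind visit;
- the number of subjects assessed as denominator, so that missing values are not read as no fall;
- the difference between each active arm and placebo with a 95% CI, by a named method suited to small counts.

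State that the cut-off is a reporting threshold that mirrors the SAP's own 10-point improvement cut-off. It is not a clinical rule and does not define the worsening mentioned in Protocol 5.3.

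The cost is one table from data already collected. The downside is one more output without multiplicity adjustment, in which some falls reflect disease progression or measurement noise, especially in the any-visit count. A footnote should say so.

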16.2 PATIENT DATA LISTINGS									
Discontinued Patients									
Listing	16.2.1.1	Discontinued Subjects Reason for Discontinuation				X			X
Listing	16.2.1.2	Visit Dates and Other Important Dates (informed consent rand date study termination)				X			X
Listing	16.2.1.3	Study Termination				X			X
Listing	16.2.2	Protocol Deviations	X						X
Patients excluded from the efficacy analysis									
Listing	16.2.3.1	Subjects Excluded from the Efficacy Analysis (Evaluability Reason for Evaluability Classification)		X			X		
Listing	16.2.3.2	Treatment Allocation and Evaluability for All Subjects		X			X		
Demographic data									
Listing	16.2.4.1	Demographic Data				X			X
Listing	16.2.4.2	Medical History				X			X
Listing	16.2.4.3	aPAP History				X			X
Listing	16.2.4.4	Inclusion Criteria Not Met and Exclusion Criteria Met				X			X
Compliance and/or drug concentration data									
Listing	16.2.5.1	Exposure				X			X

			SCR	DB-FAS	DB-PPS	DB-SAF	FU-FAS	FU-MOL INT	FU-SAF
Listing	16.2.5.2	Compliance				X			X
Listing	16.2.5.3	Rescue medication				X			X
Individual efficacy response data									
Listing	16.2.6.1	Individual Efficacy Response Data (A-a)DO2 PaO2 and Lung function tests		X			X		
Listing	16.2.6.2	Individual Efficacy Response Data 6MWT		X			X		
Listing	16.2.6.3	Individual Efficacy Response Data GM-CSF		X			X		
Listing	16.2.6.4	Individual Efficacy Response Data Anti-Drug antibodies		X			X		
Listing	16.2.6.5	Individual Efficacy Response Data Biomarkers		X			X		
Listing	16.2.6.6	Individual Efficacy Response Data DSS		X			X		
Listing	16.2.6.7	Individual Efficacy Response Data Dyspnoea score		X			X		
Listing	16.2.6.8	Individual Efficacy Response Data Cough scores		X			X		
Listing	16.2.6.9	Individual Efficacy Response Data EQ-5D		X			X		
Listing	16.2.6.10	Individual Efficacy Response Data SGRQ		X			X		
Listing	16.2.6.11	Individual Efficacy Response Data CT		X			X		
Adverse Event listings									
Listing	16.2.7.1	Adverse Event Listings by Treatment Subject Relative Day or Week				X			X
Listing	16.2.7.2	Adverse Event Listings by System Organ Class Preferred Term Treatment and Subject				X			X
Listing of individual laboratory measurements by patient									
Listing	16.2.8.1	Listing of Reference Ranges	X						
Listing	16.2.8.2	Listing of Individual Laboratory Measurements by Subject				X			X
Listing	16.2.8.3	Listing of Relevant Comments Regarding Laboratory Values				X			X
Listing	16.2.9	Vital Signs				X			X
Listing	16.2.10	Physical Examination				X			X
Listing	16.2.11	ECG				X			X
Listing	16.2.12	Concomitant Medications and Therapy				X			X

APPENDIX 2. SAMPLE SIZE RECALCULATION MOL-PAP-002

1.1 Introduction

This document describes the results from the pre-planned blinded sample size re-calculation as described in the Protocol, Final Version 5, dated 01 December 2017 (Section 12.2). The sample size calculation was planned to be in January 2018, when approximately 50 patients would have reached 24 weeks of treatment.

1.2 Methods

The blinded sample size recalculation was conducted for the following three Key secondary endpoints according to protocol

- Change from baseline to week 24 in 6MWD
- Change from baseline to week 24 in SGRQ Total Score
- Time to WLL

The change from baseline to week 24 in 6MWD [and SGRQ] were analysed in an ANCOVA model including WLL (stratification), and baseline 6MWD [SGRQ]. For the purposes of the sample size re-estimation process, only data on patients who had baseline and week 24 data was used and no imputations were made for missing values.

The minimal clinically important effect sizes for 6MWD and SGRQ in aPAP were considered to be in the order of 40-50 m and 7-10 points, respectively. From each ANCOVA model, the respective residual variance for 6MWD [and SGRQ] was used to calculate sample size based on the effect sizes of 50 m and 10 points, respectively.

The overall (pooled) event rate for WLL was determined including any patients who would meet the criteria for WLL any time prior to week 24, but excluding any patients who withdraw prior to week 24 where WLL has not been required. WLL rates of 5% (active) versus 20% (placebo) at 24 weeks was assumed, and compared to the observed (pooled) WLL rate.

All sample size calculations correspond to two group comparisons and were made based on a 2-sided 5% significance level, and 80% and 90% power. The observed SD was increased/ decreased with 10% for sensitivity. All sample size calculations were treated as independent calculations without considering that the power to reject any hypothesis is conditional on first rejecting the null hypothesis for the primary endpoint in a hierarchical manner.

If the maximum of these sample size calculations were to be no more than 33 patients per group, then no change to the target sample size would be made. Otherwise, the sample size would be increased to attain 90% power for at least 2 of the 3 key secondary endpoints, subject to the total study size not exceeding 150 patients.

The sample size calculations were done using proc Power in SAS Enterprise Guide version 7.12.

1.3 Results from Sample Size Recalculation

The sample size for SGRQ Total Score was based on an analysis of 51 subjects that had both a baseline score and a score after 24 weeks of treatment. From the ANCOVA model for change from baseline, including adjustment for strata and baseline score, the Residual Mean Square Error (MSE) was 101.582, translating to an SD of 10.1. In addition to the calculation based on the observed SD, sample sizes were also calculated assuming a 10% increase/decrease in SD.

From Table 1, it can be seen that the number of subjects needed per treatment group needs to be at least 23 in order to detect a significant difference between groups of 10 based on the observed SD with a power of 90%.

Table 1 Recalculated Sample Size to detect a difference of 10 in Total SGRQ

	Estimated Standard Deviation		
Power	9.1	10.1	11.1
80%	15	18	21
90%	19	23	27
ANCOVA MSE = 101.582 based on 51 subjects with a result at baseline and after 24 weeks.			

As for SGRQ Total Score the sample size calculation for the 6MWD was based on 51 subjects having both a baseline measurement and a corresponding measurement after 24 weeks of treatment. From the ANCOVA including adjustment for baseline and strata the estimated residual MSE was 4928.203, corresponding to an SD=70.2. For sensitivity the SD was increased/decreased with 10%. As can be seen from Table 2, based on the observed SD at least 43 subjects would be needed per treatment group in order to detect a difference of 50m between any groups with a power of 90%.

Table 2 Recalculated Sample Size to detect a difference of 50 in 6MWD

	Estimated Standard Deviation		
Power	63.2	70.2	77.2
80%	27	32	39
90%	35	43	52
ANCOVA MSE = 4928.203 based on 51 subjects with a result at baseline and after 24 weeks.			

The observed event rate of WLL was low, only 4 events among 78 randomized subjects either having WLL and then discontinuing, or subjects still remaining in trial. For the calculations it was anticipated the sample size would be calculated assuming 5% of subjects on active treatment vs 20% on placebo would have an event. Given these assumed event rates, and assuming an exponential distribution of survival times, at least 47 subjects would be needed to detect a difference between treatment groups using a log-rank test, with 80% power, and 63 subjects with 90% power, if these event rates are true. Given the low event rate, even though probably slightly underestimated in observed subjects, these calculated sample sizes are likely too optimistic.

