- ANCOVA based on the per protocol set (PPS).

Mean profiles for 6MWD and SGRQ over time will be provided.

Time to WLL during 24-weeks treatment

Kaplan-Meier plots will be used to assess time to WLL (time from randomisation to documentation of fulfilment of criterion for requiring WLL) and treatment comparisons corresponding to those made for primary endpoint, will be analysed by a logrank test adjusting for the randomisation strata (WLL). Subjects who fulfil the criteria for rescue treatment (i.e., worsening of aPAP based on symptoms, reduced exercise capacity and/or findings of hypoxemia or desaturation according to the Investigator's judgement), will be counted as if WLL was conducted at the date of fulfilment of rescue treatment criteria. In this analysis, subjects withdrawing from the trial will be handled as censored at time of discontinuation, and subjects who reach week 24 and have not needed WLL will be censored at time point for Visit at week 24. Survival estimates for time to WLL will be tabulated for subjects in each group who require WLL, by relevant time points, along with 95% Cis.

Sensitivity analyses for time to WLL will be carried out as follows:

- Any subject withdrawing from trial before week 24 and before fulfilling criteria for WLL will be handled as having WLL the day after discontinuation date. This is done to

evaluate the impact of missing data and censoring due to withdrawals. The same analyses as planned above will be conducted in order to evaluate the robustness of results with regards to the handling of censoring.

- A Cox regression will be applied where the hazard ratio and its 95% confidence interval will be estimated, while including adjustment for treatment, Japan vs other countries and WLL (stratification). The analysis will be done using the same approach for handling censoring as done in the main analysis.

Further Secondary Efficacy Analyses

The further secondary efficacy endpoints will be statistically analysed, although the analyses will be considered supportive rather than confirmatory, and will therefore not be part of the testing procedures implemented for primary and key secondary efficacy endpoints to control for multiplicity.

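### SAP Appendix 2: 47 and 63 subjects for time to WLL do not follow from 5% v 20% event rates; the log-rank test needs about 70–77 and 94–102 per group

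*SAP*

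**What the plan says.** SAP Appendix 2, section 1.2, sets common terms for the three recalculations: "All sample size calculations correspond to two group comparisons and were made based on a 2-sided 5% significance level, and 80% and 90% power". For WLL it adds that "WLL rates of 5% (active) versus 20% (placebo) at 24 weeks was assumed". Section 1.3 repeats the rates ("assuming 5% of subjects on active treatment vs 20% on placebo would have an event"), assumes exponential times and a log-rank test, and reports that "at least 47 subjects would be needed to detect a difference between treatment groups using a log-rank test, with 80% power, and 63 subjects" for 90%. It presents the sizes as valid at the assumed rates: "with 80% power, and 63 subjects with 90% power, if these event rates are true". It then notes 4 events among 78 randomised subjects and says that "these calculated sample sizes are likely too optimistic".

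Three other parts of the SAP fix the comparison being sized. Section 3.1 gives 1:1:1 allocation. Section 5.4 compares each regimen separately with placebo. Section 5.3.7 ends follow-up for this endpoint at week 24: "subjects who reach week 24 and have not needed WLL will be censored at time point for Visit at week 24". The WLL calculation states no accrual period, later follow-up, dropout or pooling of the active arms.

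**The concern.** At 47 per group these rates produce about 47 × (0.05 + 0.20) = 11.75 events. That is few for 80% power at two-sided 5%, even with a very large effect, so the figure needed checking.

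Time to WLL is one of three confirmatory key secondary endpoints. A reader who sees 47 for 80% power beside the chosen 45 per group will conclude that WLL has nearly 80% power at the assumed rates. The endpoint also matters beyond itself. Under the truncated Hochberg procedure in SAP section 5.4, rejecting only two of the three once-daily key secondary hypotheses lowers the level for the intermittent-arm primary test from 0.05 to 0.0083. The power stated for the weakest of the three therefore affects how likely the second regimen is to be tested at the full level.

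**Working it through.** **Control: the other figures in the appendix.** A two-sided 5%, 1:1 t-test with the observed SDs gives 18 and 23 per group for SGRQ (difference 10, SD 10.1), and 32 and 43 for 6MWD (difference 50 m, SD 70.2). These match Tables 1 and 2 of Appendix 2 exactly, so the common settings are understood. They also support reading 47 and 63 as per group.

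**Inputs for WLL.**
- Two-sided 5%, power 80% and 90%, event rates 5% and 20% at 24 weeks (Appendix 2, section 1.2)
- Exponential times and log-rank test (Appendix 2, section 1.3)
- 1:1 for each regimen against placebo (SAP sections 3.1 and 5.4)
- Censoring at week 24 (SAP section 5.3.7)

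**Hazard ratio.** HR = ln(0.95)/ln(0.80) = 0.0513/0.2231 = 0.230, so (ln HR)² = 2.162. The mean event probability is (0.05 + 0.20)/2 = 0.125. The factor (z for α/2 + z for power)² is 7.849 at 80% and 10.507 at 90%.

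**Schoenfeld.** Events = 4 × factor/(ln HR)².
- 80%: 4 × 7.849/2.162 = 14.5 events; 14.5/0.125/2 = 58.1, so 59 per group.
- 90%: 4 × 10.507/2.162 = 19.4 events, so 78 per group.

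**Freedman.** Events = factor × [(1 + HR)/(1 − HR)]², where the bracket squared is (1.230/0.770)² = 2.55.
- 80%: 20.0 events, so 81 per group.
- 90%: 26.8 events, so 108 per group.

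**Lakatos**, everyone followed 24 weeks: 76.1 per group (19.0 events) and 101.9 (25.5 events), so 77 and 102.

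**Two proportions**, pooled variance: 76 and 101.

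**Simulated log-rank test**, exponential times censored at week 24: 79.7–79.9% power at 70 per group and 89.5–90.1% at 94, across runs of 20,000 and 40,000.

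| Method (per group, 1:1, two-sided 5%) | 80% | 90% |
|---|---|---|
| Stated in Appendix 2 | 47 | 63 |
| Schoenfeld | 59 | 78 |
| Simulation | about 70 | about 94 |
| Two proportions | 76 | 101 |
| Lakatos | 77 | 102 |
| Freedman | 81 | 108 |

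**Power at relevant sizes**, unadjusted two-sided 5%:

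| Per group | Lakatos | Simulation |
|---|---|---|
| 45 (chosen) | 57.7% | 60.2–60.7% |
| 47 | 59.6% | 62.4–62.9% |
| 50 (cap of 150) | 62.2% | 65.1% |
| 63 | 72.2% | 75.1–76.1% |

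Schoenfeld would give 69% at 45, 71% at 47 and 83% at 63. Simulation shows that it overstates power at a hazard ratio this far from 1, so it serves only as a lenient bound on sample size.

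**What does give 47 and 63.** Several settings come close, and each conflicts with something stated:
- 5% and 20% entered as event-free proportions: Lakatos 46.9 and 62.8. This reverses the meaning of the rates.
- Uniform accrual over 1.35 × 24 weeks with follow-up to study end: 46.95 and 62.85 (46.954 and 62.858 on a finer grid). This conflicts with censoring at week 24.
- Both active arms pooled against placebo (2:1): Freedman 47.0 and 62.9 per arm, Lakatos 45.7 and 61.1. This conflicts with the separate comparisons.
- One-sided Schoenfeld: 46 and 64. This conflicts with the two-sided level, and the stated ratio 63/47 = 1.34 fits a two-sided test (10.507/7.849 = 1.339) better than a one-sided one (1.385).

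**The case against.** The best defence is that this may be an unstated setting rather than an arithmetic slip. Section 1.3 gives no allocation and speaks of active against placebo. SAP section 3.2 records that protocol versions up to 4 planned to pool the active arms. Pooled 2:1 with Freedman's formula gives the stated figures on rounding up. That possibility stands, and the cause stays open. It does not rescue the figures: section 1.2 sizes two-group comparisons, SAP section 5.4 tests each regimen separately, and the control shows 1:1 for the other two endpoints.

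Second, methods differ: the full span is 59–81 and 78–108, wider than 70–77 and 94–102. That is correct, but every method under the stated conditions is well above 47 and 63.

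Third, a power of 58–61% at 45 per group uses an unadjusted 5% level, whereas the truncated Hochberg levels are 0.0417, 0.0229 and 0.0167. Lakatos power at 45 under those levels is about 55%, 45% and 41%. The unadjusted level is the one Appendix 2 declares, but any added sentence should say so.

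Fourth, the practical effect is limited. The rule requires 90% power for only two of three endpoints. The stated 63 × 3 = 189 already exceeds the cap of 150, and nothing in the text claims that 45 per group powers WLL. All of this is true, and it limits the seriousness of the error. The caveat about optimism, however, concerns only the low observed rate, while the text still asserts the sizes at the assumed rates.

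**Conclusion.** The concern holds. Under the stated conditions, 47 and 63 do not give 80% and 90% power for time to WLL. About 70–77 and 94–102 per group are needed, by simulation and Lakatos respectively. Power at the chosen 45 per group is about 58–61%, and 90% is out of reach within the cap (about 62–65% at 50 per group). This rests on exponential times, no dropout, 1:1 comparison, follow-up ending at week 24 and unadjusted two-sided 5%. It also reads 47 and 63 as per group, the more favourable reading.

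At the observed event rate, power would be lower still, but this depends on further assumptions. Take the planned 1:4 ratio of rates and 1:1:1 allocation, so that the pooled rate is twice the active rate. Then 4/78 = 5.1% implies 2.6% v 10.3% and about 32% power at 45 per group. This is a low-end figure, because the 78 include subjects still in the trial. An illustrative denominator of 51 implies 3.9% v 15.7% and about 47–49%. The 51 are the subjects with week 24 SGRQ and 6MWD data, so 4/51 mixes two populations.

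The decision to randomise 135 stands, because 6MWD at 43 per group determines it. The correction should be made, but it does not threaten the design.

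**What to change.** In SAP Appendix 2, section 1.3:

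1. Record the settings used for the WLL calculation (group weights, accrual, follow-up, and how the rates were entered).
2. Rerun it with event-free proportions of 0.95 (active) and 0.80 (placebo) at 24 weeks, equal groups and fixed 24-week follow-up. Name the method, write that the result is per group, and replace 47 and 63 with it. Expect about 77 and 102 by Lakatos, or about 70 and 94 by simulation.
3. Add a sentence such as: At 45 per group, power for time to WLL at 5% v 20% is about 58–61% at an unadjusted two-sided 5% level; 90% power cannot be reached within the 150-patient cap (about 62–65% at 50 per group).
4. If power at the observed rate is added, give it as a range (about 32% to 49%), with the denominators and the 1:4 ratio stated as assumptions.

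The cost is one rerun and corrected text in an appendix. The target of 135, the patients and all planned analyses are unchanged.
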